**III. Study Design:**

A. *Provide a BRIEF overview of your study design and methods. The study design must relate to your stated aims/objectives. DETAILS WILL BE REQUESTED LATER. If your study also involves analysis of existing data, please complete Section XI, "Secondary Data Analysis of Existing Data" in the last part of this research plan. If your study ONLY involves analysis of existing data, please use the research plan template for secondary data analysis (JHSPH IRB Research Plan for Secondary Data Analysis of Existing Data/Specimens).*

This study is a randomized control pilot trial testing the DPP Cooks against standard DPP. DPP is a 12 month diabetes prevention behavioral weight loss program developed by the CDC and implemented

nation wide. Participants meet weekly for the first 6 month in group sessions, then meet less frequently over the last 6 months to help them maintain the behavioral changes (re: diet and physical activity) they made in the first six months. For this trial, up to 48 participants will be randomized 1:1 to participate in the 12 month DPP or the 12 month DPP *plus* an additional 6 cooking skills sessions (DPP Cooks) during the first 4 months of the DPP. The primary outcome, weightloss, is collected at weekly DPP sessions. The secondary outcomes will be collected via online surveys at baseline, 4 months and 12 months, and via the Remote Food Photography Method (RFPM) at baseline and 4 months.

- B. *Provide a sample size and a justification as to how you arrived at that number. If you use screening procedures to arrive at a final sample, distinguish the screening sample size from the enrolled sample size; a table may be helpful. For electronic survey studies involving online recruitment and survey completion: consider how you will set controls on how many people will join your study.*

The target sample size of 48 individuals, randomized 1:1 was based on the fact that this is a pilot feasibility trial so we are not necessarily concerned with detecting statistically significant results. Budget constraints preclude a higher sample size. This sample size will allow us to test the DPP Cooks with several cohorts to understand implementation and prepare for a larger, fully powered study in the future.

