Diet quality will be collected by the participant by taking photographs of all the food they eat over a 3-day period and uploading those photographs to the SmartIntake app. Participants will be reminded to do this based on text messages from the study team, and the study team will be on hand to assist participants if they run into any problems or need help. Participants will be given a reference card to include in food photographs (e.g. a blank white card with some lines on it to help gauge portion size as well as a paper food tracker and guidebook). Other measures of interest will be collected using online surveys (Qualtrics) at baseline, 4 months and 12 months. Finally, we will invite participants to share their thoughts and experiences with the DPP Cooks intervention in in-depth interviews (over Zoom or phone) at the end of the study (12 months).

]

- [ ]
3. *Describe the expected duration of the study from the perspective of the individual participant and duration overall.*

[The duration of the study is 12 months from start to finish. From the participant's perspective they will attend DPP sessions and some participants will have 6 extra cooking classes. Data collection will not require in person study visits. The participant will have a training session with study team staff to help them install and learn how to use the RFPM app and record their data. This session will take place over zoom before baseline data collection begins.

]

4. *Provide a brief data analysis plan and a description of variables to be derived.*

[The key independent variable for all analyses is an indicator of whether or not the participant is in the control (standard DPP) group or the intervention (DPP Cooks) group. The other key variable is an indicator of time (baseline, 4 months, or 12 months). The primary outcome variables are weight loss (in kg lost, and in % of body weight lost). The secondary outcome variable is dietary intake/quality. We will use the data from the RFPM to calculate Healthy Eating Index-2015 scores. We will also be able to measure fruit and vegetable, as well as carbohydrate intake. Additional secondary outcomes from survey measures will include cooking confidence, cooking attitudes, cooking behaviors, cooking skills, food agency, and food security status. For most analyses we will compare changes in scores from baseline to 4 months and baseline to 12 months between intervention and control groups.]

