**IX. Payment or Token of Appreciation:**

- A. *Do you plan to provide a non-monetary token of appreciation (food, soap, tea, chlorine tablets, etc.) to study participants? If no payment is provided, the JHSPH IRB strongly encourages providing such tokens. If yes, please describe below.*

[DPP Cooks participants will receive a Participant Workbook (attached) that will accompany and serve as a resource for the cooking classes. They will also receive food for the recipes that will be cooked at each class and will be able to take any left over food home with them. In the standard DPP arm, participants will also be offered the Participant Workbook and a cooking class (with accompanying food) at the conclusion of the 12 months. Participants who opt in will also be provided a CGM for 14 days at baseline and 12 months.]

]

- B. *If you plan to provide a monetary payment, describe the form, amount, and schedule of payment to participants. Reimbursement for travel or other expenses is not “payment,” and if the study will reimburse, explain.*

[ All participants will be compensated \$100 (\$20 after baseline data is completed, \$20 after 4 month data collection is completed, and \$60 after 12 month data collection is completed). ]

- C. *Include the possible total remuneration and any consequences for not completing all phases of the research.*

[ If participants do not complete all phases of the study they will only be compensated for the phases they did complete. ]

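### The 12-month survey comparison has no stated model or missing-survey rule; run as simple change scores, it could be biased in either direction if early response or its link to dropout differs by arm

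*Combined protocol and SAP*

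**What the plan says.** The whole analysis plan is item 4 of section V.C. Besides study arm it names one further key variable: "The other key variable is an indicator of time (baseline, 4 months, or 12 months". For most analyses, it says, "we will compare changes in scores from baseline to 4 months and baseline to 12 months between intervention and control groups". The survey scores are secondary: "Additional secondary outcomes from survey measures will include cooking confidence, cooking attitudes, cooking behaviors, cooking skills, food agency, and food security status".

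The schedule is given in section V.C.2: "Other measures of interest will be collected using online surveys (Qualtrics) at baseline, 4 months and 12 months". A participant can therefore have a 4-month score and no 12-month score.

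No section names a test or model, an analysis population, an expected attrition rate or a way of handling missing surveys. Incomplete participation appears only in the payment rule of section IX.C, where participants who stop early are told "they will only be compensated for the phases they did complete".

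On size, section III.A says "up to 48 participants will be randomized 1:1 to participate in the 12 month DPP". Section III.B rests this on pilot status and budget, adding that "we are not necessarily concerned with detecting statistically significant results". Section V.C.5.A makes the DPP cohort the unit of randomization, and section V.C.1 puts 8 to 12 people in a cohort.

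**The concern.** A change from baseline to 12 months exists only for someone who returns the 12-month survey. If the two planned contrasts are computed as two separate change-score comparisons, everyone else leaves the 12-month one, and their 4-month answers play no part in it.

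That matters if staying in the study is related to early progress and the relation is not the same in both arms. A difference by arm is plausible. Only DPP Cooks has six extra 2-hour classes in the first 4 months and text messages in the 8 months after, and participants will know which they attend. The classes aim at the very things that the survey measures: cooking skills, confidence and food agency. So early response, or its link to staying, could differ between arms. The 12-month contrast would then partly reflect who stayed. Since section III.B presents the pilot as preparation for a larger study, a distorted 12-month estimate could carry into that design.

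**Working it through.** The stated size of 48 has no alpha, power, effect or SD behind it, so there is no figure of the plan to reproduce. The question is how large the bias could be.

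**Inputs.** From the documents: 48 participants at 1:1, so 24 per arm; surveys at baseline, 4 and 12 months. Assumed, because the documents give nothing: scores with SD 1; correlation 0.5 of baseline with each follow-up; correlation r of 0.5 or 0.7 between 4 and 12 months; all 4-month surveys returned. In one arm (DPP Cooks first), 40% or 50% of those below that arm's mean 4-month gain and 10% of those above it miss the 12-month survey. The other arm loses 20-25% at random.

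**Step 1: selection among completers.** With half the arm on each side of the mean, the average standardized 4-month gain among completers is √(2/π) × (kept above − kept below) / (kept above + kept below).
- 40%/10% loss: 0.798 × (0.9 − 0.6)/(0.9 + 0.6) = 0.160
- 50%/10% loss: 0.798 × (0.9 − 0.5)/(0.9 + 0.5) = 0.228

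**Step 2: carry-over to the 12-month change.** The covariance of the two changes is r − 0.5 − 0.5 + 1 = r. The SD of the 4-month gain is √(2 − 2 × 0.5) = 1. So the bias is r times the value in step 1. The table sets this beside simulated results (6,000 trials per setting, true 12-month effect 0.4 SD); bias is in SD of the score.

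| r | Loss below/above mean gain | Completer change, by formula | Completer change, simulated | Completers with baseline covariate, simulated | Repeated-measures model using 4-month scores, simulated |
|---|---|---|---|---|---|
| 0.5 | 40%/10% | 0.080 | 0.082 | 0.044 | 0.004 |
| 0.5 | 50%/10% | 0.114 | 0.117 | 0.061 | 0.003 |
| 0.7 | 40%/10% | 0.112 | 0.109 | 0.067 | −0.004 |
| 0.7 | 50%/10% | 0.160 | 0.161 | 0.106 | 0.001 |

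**Step 3: change which arm is affected.** The same selective loss in the control arm only gives about −0.09 to −0.15 SD by simulation. The same rule in both arms gives 0.00 to −0.01.

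**Step 4: a different dropout model.** Here the chance of a missing 12-month survey varies smoothly with 4-month change (logistic, slope 1.5 per SD), with 10%, 20%, 30% and 40% missing overall and all correlations 0.5.
- Missing completely at random: about 0.
- Same mechanism in both arms, no true effect: at most 0.011.
- Same mechanism, true effect 0.5 SD at both times: −0.03, −0.04, −0.06, −0.07. With a 4-month effect of 0.8 SD: −0.05, −0.07, −0.09, −0.11.
- One arm only, no true effect: +0.06, +0.12, +0.17, +0.20.
- Opposite directions in the two arms, no true effect: +0.12, +0.22, +0.33, +0.42. This is an extreme case that nothing in the documents suggests.

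The repeated-measures estimate stayed within about 0.01 SD of the truth throughout. That is expected, since loss was made to depend only on observed scores.

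**Step 5: set against sampling error.** A loss of 25% leaves 24 × 0.75 = 18 per arm. The change score has SD 1, so the standard error is √(1/18 + 1/18) = 0.33. The largest bias in the table is 0.16/0.33 = 0.48 of a standard error.

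**Step 6: where precision comes from.** Adjusting for baseline cuts the residual SD to √(1 − 0.5²) = 0.87, so the standard error becomes 0.87 × 0.33 = 0.29. Simulated values were 0.33-0.35 for completer change, 0.29-0.31 for completers with a baseline covariate, and 0.28-0.30 for the joint model. The 4-month scores add only 0.00-0.02. None of these figures allows for clustering by cohort.

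**The case against.** The strongest reply is that the plan never says that it will drop anyone. It lists a three-level time indicator, which a simple change-score comparison does not need but an arm-by-time repeated-measures model does. The two planned contrasts could be read from such a model. This stands: a reader might infer a completers-only analysis, but the text leaves the estimator open. What remains is that the choice is unstated and could be made after the data are seen.

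A reader might also infer that dropout driven by early response is enough to bias the result, or that it would flatter DPP Cooks. Neither is supported. Under a common rule with similar early gains the bias is about zero, selective loss in control alone reverses the sign, and a common mechanism with a real early benefit understates the effect. Nothing in the documents says which case will occur.

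It is fair, too, that heavy loss is not a given. Section IX.C is a conditional payment rule and no forecast of attrition. Of the $100 payment, $60 follows the 12-month data; eligibility requires a 12-month commitment; and the surveys are online. Finally, these are additional secondary outcomes in a pilot that does not aim at significance. That limits the weight of the point but does not remove it, because the better analysis needs no new data.

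**Conclusion.** The point holds as a gap in specification with a cheap remedy. The plan gives two change-score contrasts and no model or missing-survey rule. If they are run literally, the 12-month survey comparison rests on completers and can be biased when early response, or its link to dropout, differs between arms.

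Under assumed one-arm loss of 40-50% versus 10% by early gain, the bias is about 0.08-0.16 SD in absolute size, of unknown sign and at most about half a standard error. With the same rule in both arms and similar early gains it is about zero. Every rate and correlation is an assumption, and the calculation takes all 4-month surveys as returned. The primary outcome, weight, is not part of this point.

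**What to change.** For each survey score, specify one repeated-measures model fitted to all randomized participants with at least one follow-up survey:
- 4- and 12-month scores as outcomes, with the baseline score as covariate;
- arm, time and arm by time, with unstructured within-person covariance;
- a small-sample correction;
- the DPP cohort structure of section V.C.5.A accounted for.

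Read both arm differences from this model, and report the completer change-score comparison as a sensitivity analysis. The food-photograph record has a single follow-up and gains nothing from the 4-month feature.

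The cost is plan wording and modest programming. Under the assumptions above, the standard error falls from about 0.33-0.35 to 0.28-0.30 SD before clustering, mostly through baseline adjustment.

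There are limits. The model is less simple at 48 participants, and with 8 to 12 people per cohort there are only about 48/12 = 4 to 48/8 = 6 cohorts from which to estimate a cohort effect. It still assumes that loss depends on observed scores, and it does not help for people lost before month 4.

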**JHM Preferred:**

- JH SAFE Desktop  JH PMAP

**Other Approved Platforms:**

- JH One Drive/JHSPH OneDrive  JH IT-Managed Network Storage  JHM/JHSPH Qualtrics  
 JHSPH HPCC  JHSPH SharePoint  JHSPH Shares  JHU REDCap  
 MARCC-Secure Environment

- Platform(s) not managed by JH/JHSPH, not pre-approved, and require a risk assessment review from JHSPH Data Security (*please describe*): Pennington team (subcontract) will be responsible for analyzing the dietary data collected by the participant using the SmartIntake app. Data is transferred automatically and is stored and managed on the ADMU.

- Describe risk mitigation measures that are in place: Data transferred and stored is deidentified. Any communication with the JHU team and Pennington will reference participants by their ID number not by name or other identifying information.

Note: The following are examples of platforms/storage solutions that are **not pre-approved to store identifiable information** and require a risk assessment from JHSPH Data Security:

- Other solutions not managed by IT@JH, e.g., commercial cloud storage (Box, Dropbox, iCloud, personal OneDrive, Google Drive, Amazon storage, etc.)
- JHU Independent Departmental Servers
- Local Computer owned by JH
- Other computers or devices owned/managed by study team members and used for other than secure web access
- USB/Portable data storage device

**10. Access to Data and Access Controls:** How will you ensure that only authorized individuals can access the data? What access controls will you put into place to ensure that only authorized individuals may access and use the data. (For example, OneDrive [guidance](#) illustrates how to share files with “people you specify”. [JHSPH-Shares](#) addresses providing permissions to individual people.) Check all that apply. Note: If you need assistance implementing secure access controls, contact [jhsph\\[contact]](mailto:[contact]).

- Will provide access to data in accordance with OneDrive/JHSPH-Shares guidance posted on JHU IT websites
- Will use secure access controls to limit access to individual-level data
- Will use secure access controls to provide other researchers controlled access only to aggregated study data

**11. Data Sharing:** Clarify if data are to be shared externally with third parties, including sponsors and other investigators, and whether only aggregated data will be shared, or if you will share individual-level data. Describe sharing and protection plans for that sharing, including the proposed use of data agreements.

Consider the following:

- Information about your data sharing in the consent forms
- Information about data sharing laws in the country where data will be collected, and if they limit sharing, how you will comply with those limitations?
- Whether data will be shared in aggregate only, or individual level data
- Whether you plan to make the data publicly available, and in what form.

Will not share data with outside investigators

Will share aggregated data only

Will share individual-level data without identifiers

Will deposit data into an existing data repository for future research (*explain*):

Other sharing information: [            ]

**12. Duration and Destruction:** Explain how long data will be retained and the plan for eventual return, deidentification or destruction of data, including moving data to an archive.

[ We will retain all deidentified study data for at least 4 years to use to publish manuscripts and to have on hand for additional analyses we may need to conduct to support applications for future funding. Any identifiers will be deleted as described above.            ]

**A. Certificate of Confidentiality:**

All NIH studies include Certificate of Confidentiality (C of C) protections with the grant; the consent form must include the C of C language provided in our template. Other funders may obtain C of C protections through NIH. (<https://grants.nih.gov/policy/humansubjects/coc.htm> )

Does the study have Certificate of Confidentiality protections? [Yes  No

**VII. Risks of the Study:**

- A. Describe the risks, discomforts, and inconveniences associated with the study and its procedures, including physical, psychological, emotional, social, legal, or economic risks, and the risk of a breach of confidentiality. Include risks beyond individuals to include the study population as a group and community risks. Ensure that the risks described in the consent documents are consistent with the risks outlined in the research plan.

[The risks of harm or discomfort that may happen as a result of taking part in this study are not expected to be more than in daily life. It is possible that there is some risk of injury (minor cuts or burns) during the hands-on cooking classes. However, these risks are no greater than during regular

daily food preparation. There may also be risk of food allergy events during the cooking classes, but again, this risk is no higher than in daily life. As with all data collection, there is the possibility of breach of confidentiality.

- B. *Describe steps you will take to mitigate or minimize each of the risks described above. Include a description of your efforts to arrange for care or referral for participants who may need it.*

[ The DPP is a proven intervention that has been widely implemented nationally. In this study, the DPP is not being modified in any way and will be conducted by DPP Coaches without any involvement from the study team. To protect against potential breach of confidentiality, all data will be immediately de-identified and only participant ID codes will be used on all quantitative and qualitative data. The spreadsheet linking participant ID codes to participant's identifying information will be stored separately in the JHU OneDrive. No names or other identifying information will ever be used in any publication or dissemination materials. All study data will be stored on locked, password protected computers equipped with two-factor identification systems for the OneDrive. Risks of injury during the cooking classes is minimal, but study staff and the chef instructor will have first aid kits on hand to handle any minor cuts, burns or other injuries. In addition, kitchen safety and safe knife handling will be emphasized during the classes. To avoid food allergy events, prior to any food tasting or cooking activities we will ask participants about any known food allergies, and will clearly identify all ingredients in the recipes we prepare and taste. ]

- C. *Describe the anticipated frequency and severity of the harms associated with the risks identified above; for example, if you are performing "x" test/assessment, or dispensing "y" drug, how often do you expect an "anticipated" adverse reaction to occur in a study participant, and how severe do you expect that reaction to be?*

[ We do not anticipate any of the risks involved would be greater than those expected during daily life. ]

- D. *Describe the research burden for participants, including time, inconvenience, invasion of privacy in the home, out of pocket costs, etc.*

[ Participants will participate in the DPP (at least 16 weekly sessions of the first 6 months and at least 6 sessions in the last 6 months) and in the DPP Cooks arm will also participate in 6 2-hour cooking classes over the first 4 months. Participants will answer surveys at 3 time point, will complete 3 days of dietary recall (by taking pictures on their smart phone) at 2 time points, and will have the option to wear a CGM for 14 days at 2 time points. They will also have the option to participate in an in-depth interview after the completion of the program. In total, data collection activities should be a minor inconvenience and time commitment. Invasion of privacy is a very low risk and we do not anticipate any out of pocket costs. ]

- E. *Describe how participant privacy, and if relevant – family privacy - will be protected during data collection if sensitive questions are included in interviews, or if study visits occur in the home setting.*

[ Sensitive questions are not included in any data collection documents and there are no in person or in home data collection activities. ]

]

**VIII. Direct Personal and Social Benefits:**

- A. *Describe any potential direct benefits the study offers to participants (“payment” for participation is not a direct personal benefit).*

[All participants will complete the DPP and will gain knowledge and social support to lose weight and improve their risk of developing type-2 diabetes. Participants in the cooking classes will also gain knowledge and skills related to healthy cooking and food agency. Participants in the DPP only arm will be offered the opportunity to ask take one of the cooking classes as well at the conclusion of the study.]

- B. *Describe potential societal benefits likely to derive from the research, including value of knowledge learned.*

[More than 30 million Americans have diabetes and another 84 million have pre-diabetes. Diabetes is a leading cause of mortality and morbidity and disproportionately affects low-income and racial/ethnic minority populations. Findings from this study may identify potentially important modifications to the DPP that could improve our ability to prevent type-2 diabetes. Procuring and preparing food is a daily occurrence and this study will provide new, detailed, and directly observed information that will inform not only the DPP Cooks intervention but that may be useful to create new or improve existing cooking interventions aims at building cooking skills necessary for consumption of a healthy diet. Overall, this study may produce new knowledge that will be important for improving diet quality and preventing diabetes and other diet related diseases.]

]

